### **Healthy Comparison Adolescents**

### *Inclusion criteria:*

- Females.
- Adolescents ages 12-18,
- Speak English.

	Protocol Title:	Reward Systems and Food Avoidance in Adolescents with
	Trotocor ritie.	
		Low Weight Eating Disorders
M	Principal Investigator	[name]
///X	Name/Contact Info:	[contact]; [contact]
Mount	Primary Contact	[name]
Sinai	Name/Contact Info	[contact]; [contact]
	Date Revised:	
	Study Number:	GCO#15-0939 IF# 2446156 HS# 16-00570

#### Exclusion criteria:

- Current psychotropic medication that would have an effect on performance on behavioral tasks (i.e., stimulant medication),
- Current or lifetime history of any psychiatric disorder, including eating disorders by K-SADS,
- Current or lifetime history of learning disorder or developmental disability
- Active suicidal ideation,
- Major medical illness,
- Other physical limitation that would prevent participation (e.g., allergic to chocolate).

## c) Number of Subjects

A total of 118 female adolescents will be recruited to obtain complete assessments on 60 female adolescents with a low weight ED and 30 healthy comparison adolescents between the ages of 12-18.

## d) Study Timelines

Participants' participation will include 10 visits over approximately 8-week period for AN participants and 4 visits for healthy comparison controls. During the 6 weeks separating the testing, adolescents with low weight EDs will receive an intervention (please see below), whereas healthy comparison adolescents will not have additional contact with study staff during this time.

Visit 1 will consist of screening procedures to determine eligibility, completion of self-report questionnaires, and a laboratory based eating measure.

In Visit 2, all participants will complete a reversal learning computerized task while undergoing an fMRI scan with EMG, computerized task also using EMG, and lastly the completion of a multi-item meal task in which we will analyze eating behavior via video recording and facial recognition software.

The next 6 visits will only apply for **LW-ED participants and not healthy controls** and will consist of the exposure-based intervention, across a span of 6 weeks. Participants will be randomized into one of two intervention groups, a weight gain control group and an interoceptive exposure group.

In Visit 9, all participants will complete self-report measures, single item meal task, and height and weight.

Protocol Title:	Reward Systems and Food Avoidance in Adolescents with	
	Low Weight Eating Disorders	
Principal Investigator	[name]	
Name/Contact Info:	[contact]; [contact]	
Primary Contact	[name]	
Name/Contact Info	[contact]; [contact]	
Date Revised:		
Study Number:	GCO#15-0939 IF# 2446156 HS# 16-00570	

In Visit 10, all participants will complete the same self-report questionnaires, concurrent fMRI--EMG, and computerized learning task, and the multi-item meal task.

After the 10 visits, LW-ED participants are offered 20 sessions of free open-label family-based treatment.

The duration anticipated to enroll all study subjects is 42 months [~1.5 LW-ED patients per month with 60 enrolled by ~month 40 (2 months start-up)], leaving 6 months to analyze the data.

The anticipated duration of the study is 4 years.

The study is estimated to be completed 4 years from the date of initial IRB approval.

# e) Study Endpoints

The study is estimated to be completed 4 years from the date of initial IRB approval including months 43-48 for data analysis.

# f) Procedures Involved in the Human Research

All tests and procedures being performed are completely research-related and are not part of clinical care. LW-ED participants will complete Visits 1-10 while healthy comparison adolescents will only complete the Baseline Assessments (Visits 1 and 2) and the final two visits (Visit 9, and 10). The total timeline for participation is approximately 9 weeks.

The study will be described to interested participants (or parents) and the first of two baseline assessment sessions will be scheduled. Participants with low weight EDs will not be enrolled into the study until clearance to receive outpatient therapy has been received from her pediatrician. We will provide a medical clearance form with guidelines for the necessary tests to determine if participants can be seen on an outpatient basis. If necessary, participants may be further medically evaluated by a psychiatrist on staff. The psychiatrist will provide feedback and facilitate the coordination of care if medical evaluation reveals abnormalities.

Protocol Title:	Reward Systems and Food Avoidance in Adolescents with
	Low Weight Eating Disorders
Principal Investigator	[name]
Name/Contact Info:	[contact]; [contact]
Primary Contact	[name]
Name/Contact Info	[contact]; [contact]
Date Revised:	
Study Number:	GCO#15-0939 IF# 2446156 HS# 16-00570

Baseli	ne	Session 1 of IE or FBT	Session 2 of IE or FBT	Session 3 of IE or FBT	Session 4 of IE or FBT	Session 5 of IE or FBT	Session 6 of IE or FBT	Post-Tre	atment
Visit 1 (Day 0)	Visit 2 (Day 1-7)	Visit 3 (Day 14)	Visit 4 (Day 21)	Visit 5 (Day 28)	Visit 6 (Day 35)	Visit 7 (Day 42)	Visit 8 (Day 49)	Visit 9 (Day 50-57)	Visit 10 (Day 57- 80)
		2 hours	1 hour						
Eligibility 1) Consent/ Assent 2) K-SADS 3) EDA-5 4) C-SSRS	fMRI- EMG 1) reversal food-cue learning 2)disgust conditioni ng task	Video Coding	Video Coding	Video Coding	Video Coding	Video Coding	Video Coding		fMRI-EMG 1) reversal food-cue learning 2)disgust conditionin g task
Self-Report Measures (6): 1) CIA 2) DSR 3) ASI-III 4) BAQ 5)CES-DC 6) YEDE-Q	EMG- behavior reversal \$\$-cue learning							Self-Report Measures (6): 1) CIA 2) DSR 3) ASI-III 4) BAQ 5)CES-DC 6) YEDE-Q	EMG- behavior reversal \$\$-cue learning
Lab eating paradigm (meal replacement shake)	Lab eating paradigm (multi- item meal)							Lab eating paradigm (meal replacement shake)	Lab eating paradigm (multi-item meal)
Height/ Weight								Height/ Weight	
	Real World Eating Food records collected								Real World Eating Food records collected

The Baseline Assessment includes Visits 1-2:

# Visit 1 (2 hours total)

This is an in-person screening visit to determine eligibility.

Protocol Title:	Reward Systems and Food Avoidance in Adolescents with
	Low Weight Eating Disorders
Principal Investigator	[name]
Name/Contact Info:	[contact]; [contact]
Primary Contact	[name]
Name/Contact Info	[contact]; [contact]
Date Revised:	
Study Number:	GCO#15-0939 IF# 2446156 HS# 16-00570

#### Consent/Assent Process:

• Conducted with a trained member of the research team (project coordinator or study therapist). In order for the adolescent to participate in the study, at least one parent or guardian must participate in intervention sessions. Any parent(s) who will be involved in the intervention will sign an informed consent document and written assent will be obtained from all adolescents.

#### Assessments:

- EDA-5 for eating disorder diagnoses and psychopathology.
- Relevant sections of the *K-SADS* (mania, psychosis, alcohol and substance abuse) to determine any lifetime psychiatric disorder to determine eligibility.
- Columbia-Suicide Severity Rating Scale (C-SSRS) to assess for suicidal ideation.

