#### Exclusion criteria:

- Current psychotropic medication that would have an effect on performance on behavioral tasks (i.e., anti-anxiety medication),
- Comorbid psychotic or bipolar disorder,
- Active suicidal ideation,
- Major medical illness known to influence eating or weight,
- Current substance dependence,
- Previous exposure therapy for LW-ED.
- Physical limitation that would prevent participation (e.g., allergic to chocolate),
- For patients with current or a history of sexual or physical abuse by parents, siblings, or guardians, perpetrators of the abuse will be excluded from treatment; if physical or sexual abuse by a family member occurs during the course of treatment, perpetrators will be excluded from ongoing treatment

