### Self-Report

- Clinical Impairment Assessment (CIA)
- Disgust Scale-Revised (DSR)
- Anxiety Sensitivity Index-III (ASI-III)
- Body Awareness Questionnaire (BAQ)
- Center for Epidemiological Studies Depression Scale for Children (CES-DC)Youth Eating Disorder Examination-Questionnaire (YEDE-Q)

We will have a trained study coordinator review medical clearance from the participant's physician, consistent with our clinic's procedures for outpatient care.

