## If found eligible after these assessments, the participant will complete the single-item meal and will be scheduled for Visit 2.

Single-Item Meal: A standardized laboratory test meal will be used as an objective assessment of food avoidance in adolescents with LW-EDs. The meal consists of a strawberry yogurt shake used previously in a study of AN by [name] (Co-I)(30). Limited intake observed in this test meal before and after intensive inpatient treatment and subjective reports of anxiety by patients suggest the utility of this paradigm for LW-EDs. Procedures are based on those described by Sysko et al.(30, 31), and will be identical for experimental IE sessions. Participants will be presented with an 55 fluid ounce (1626.50-mL) covered opaque container containing approximately 1475 grams (1 kcal per gram, or 1475 kcal) of strawberry yogurt shake. Patients will be informed that the meal consists of a strawberry yogurt shake, but will not be told the amount provided in the container. The instructions will direct participants to consume as much of the shake as they would like and that the meal will serve as their lunch (or dinner) for the day and to avoid touching or manipulating the container in any way. The meal will be placed on a modified

Protocol Title:	Reward Systems and Food Avoidance in Adolescents with
Trotocor ritie.	Low Weight Eating Disorders
Principal Investigator	[name]
Name/Contact Info:	[contact]; [contact]
Primary Contact	[name]
Name/Contact Info	[contact]; [contact]
Date Revised:	
Study Number:	GCO#15-0939 IF# 2446156 HS# 16-00570

[figure not shown]
version of an eating monitor, which measures intake (in g) every 5 s. During the meal, participants will also be observed through a closed-circuit video monitor to ensure that they are following instructions and to monitor behavior. Ratings will be made before and after the test meal of hunger, fullness, sickness, loss of control, urge to eat, preoccupation with thoughts of food, disgust, and fear of fatness on a 15-cm visual analog scales (VAS). Consumption of the shake in Kcal will be the primary outcome, with secondary outcomes of rate of eating in Kcal/min during the 30 min meal.

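### The K-SADS sections listed for Visit 1 are too narrow to apply the healthy-control exclusion for any lifetime psychiatric disorder

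*Protocol*

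**What the plan says.** Section 5(b) of the protocol sets different psychiatric exclusions for the two groups. Healthy comparison adolescents are excluded for "Current or lifetime history of any psychiatric disorder, including eating disorders by K-SADS". For patients with a low-weight eating disorder the diagnostic exclusions are narrower: "Comorbid psychotic or bipolar disorder" and "Current substance dependence".

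Section 5(f), Visit 1, Assessments, lists three instruments: the EDA-5 for eating disorders, the C-SSRS for suicidal ideation, and the relevant sections of the K-SADS, named in brackets as "mania, psychosis, alcohol and substance abuse) to determine any lifetime psychiatric disorder to determine eligibility". The list is not divided by group. Section 5(f) has controls complete Visits 1 and 2 and the final two visits, and Visit 1 is the screening visit for everyone.

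The schedule table's eligibility cell reads "Eligibility 1) Consent/ Assent 2) K-SADS 3) EDA-5 4) C-SSRS" and names no K-SADS sections. The questionnaires, including the CES-DC and ASI-III, are in a separate self-report cell. The Visit 1 text then continues: "If found eligible after these assessments, the participant will complete the single-item meal and will be scheduled for Visit 2".

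**The concern.** The control criterion covers every current or lifetime psychiatric disorder. The interview that has to apply it covers three diagnostic areas, yet the same sentence says those areas determine any lifetime disorder. The sentence therefore conflicts with itself and with section 5(b).

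The first of the two primary research questions, and Aims 1 and 2, compare patients with controls. That contrast is not randomised, so its meaning depends on the control group being what section 5(b) says it is. The protocol's Background itself links aversive conditioning and extinction to mental illness broadly, so the disorders left unassessed are plausibly related to what the scans and tasks measure.

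**Working it through.** No calculation can test this, so the check compares what the control criterion requires with what Visit 1 supplies.

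| Required by the control exclusion, section 5(b) | Listed assessment at Visit 1, section 5(f) |
|---|---|
| Bipolar disorder | K-SADS, mania section |
| Psychotic disorder | K-SADS, psychosis section |
| Alcohol and substance disorders | K-SADS, alcohol and substance section |
| Eating disorders | EDA-5, although the criterion names the K-SADS |
| Depressive disorders, lifetime | None (CES-DC is a self-report scale) |
| Anxiety disorders, lifetime | None (ASI-III is a self-report scale) |
| Obsessive-compulsive disorder, lifetime | None |
| Attention disorders, lifetime | None |

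The C-SSRS serves the separate exclusion for active suicidal ideation.

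**Which criterion the listed sections fit.** Mania, psychosis and substance abuse correspond to the patient exclusions, "Comorbid psychotic or bipolar disorder" and "Current substance dependence". They do not span the control exclusion.

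**Whether the reading of the criterion matters.** The K-SADS reference could govern the whole criterion or only the eating disorders. On the first reading, the sections given are too few. On the second, the other disorders have no named instrument at all, and the instrument named for eating disorders differs from the one used. The gap remains on either reading.

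**Whether the questionnaires close it.** Section 5(d) separates the two activities: "Visit 1 will consist of screening procedures to determine eligibility, completion of self-report questionnaires, and a laboratory based eating measure". The schedule does the same and repeats the questionnaires at Visit 9 as outcome measures. No cut-off or eligibility role is given for them, and the protocol does not use them to establish a lifetime diagnosis.

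**Whether other sections close it.** The safety-monitoring section mentions the K-SADS only for psychotic symptoms. It also says what to do if a disorder such as major depression is discovered. The withdrawal section allows discharge of a patient who meets an exclusion criterion. Neither supplies an assessment that would find the disorder.

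**Arithmetic that the document allows.**
- Section 5(c) plans complete assessments on 30 controls, so one misclassified control is 1/30 = 0.033, or 3.3% of the comparison group.
- Visit 1 lasts 2 hours and the single-item meal 30 minutes, so 120 − 30 = 90 minutes remain for consent and assent, the three interviews and six questionnaires.

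**The case against.** The strongest reply is that this is a slip in a list rather than a gap in screening. The sentence speaks of relevant sections, which could differ by group, and its stated purpose matches the control criterion, since lifetime history is required only of controls. The protocol uses bracketed examples loosely elsewhere, and the schedule lists the K-SADS without restriction. Several other exclusions, such as learning disorder or medication use, have no named instrument and are presumably established by history. Section 4 gives a clinical psychologist and a post-doctoral fellow diagnostic interviewing duties that are not limited to three areas, and the safety section expects that major depression may come to light during evaluation. The details of which modules are given could sit in a procedures manual.

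Part of this stands. Staff may in practice give more sections than are listed, and the text cannot show what they do. The direction of any bias is an assumption, and 3.3% is a weight per person, not an effect size.

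It does not remove the point. The bracketed list carries no sign that it is only illustrative. The role descriptions name no wider assessment, and incidental discovery is not screening. If more sections are in fact given, the protocol misdescribes its own eligibility procedure and still needs correcting. Nor can an analysis plan repair this later, because it cannot recover diagnoses that were never assessed.

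**Conclusion.** The concern holds. As written, the Visit 1 procedure cannot apply the control exclusion to depressive, anxiety, obsessive-compulsive or attention disorders, so controls with a current or past disorder of these kinds can be enrolled against the protocol.

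The effect on Aims 1 and 2 cannot be sized, because the protocol gives no prevalence, SD or effect size for these outcomes. Dilution of the contrast is the likely direction if such controls resemble patients more than unaffected controls do; that is an assumption. No loss of power is claimed. The randomised IE versus FBT-WG comparison is untouched because controls are not in it. The change should be made: it is small, and it secures the comparison group for a primary research question.

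**What to change.** In section 5(f), Visit 1, Assessments, state the K-SADS sections separately by group. Keep the listed sections for patients, and give controls the full screening interview or all the sections needed to apply their exclusion in section 5(b). In the same edit, name one instrument for eating disorders in controls, since section 5(b) says K-SADS and section 5(f) uses the EDA-5. Carry the group-specific wording into the eligibility cell of the schedule table. Narrowing the criterion to what is now assessed would also make the text consistent, but it would change who counts as a healthy control.

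The cost is a longer interview for at least the 30 controls to be completed, with an instrument already in the study. The protocol gives no duration for the interviews or questionnaires, so whether they still fit in the 90 minutes outside the meal must be checked. Some controls who now pass would fail screening, so somewhat more may have to be screened; how many is not known.

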### Self-Report

- Clinical Impairment Assessment (CIA)
- Disgust Scale-Revised (DSR)
- Anxiety Sensitivity Index-III (ASI-III)
- Body Awareness Questionnaire (BAQ)
- Center for Epidemiological Studies Depression Scale for Children (CES-DC)Youth Eating Disorder Examination-Questionnaire (YEDE-Q)

We will have a trained study coordinator review medical clearance from the participant's physician, consistent with our clinic's procedures for outpatient care.

## If found eligible after these assessments, the participant will complete the single-item meal and will be scheduled for Visit 2.

Single-Item Meal: A standardized laboratory test meal will be used as an objective assessment of food avoidance in adolescents with LW-EDs. The meal consists of a strawberry yogurt shake used previously in a study of AN by [name] (Co-I)(30). Limited intake observed in this test meal before and after intensive inpatient treatment and subjective reports of anxiety by patients suggest the utility of this paradigm for LW-EDs. Procedures are based on those described by Sysko et al.(30, 31), and will be identical for experimental IE sessions. Participants will be presented with an 55 fluid ounce (1626.50-mL) covered opaque container containing approximately 1475 grams (1 kcal per gram, or 1475 kcal) of strawberry yogurt shake. Patients will be informed that the meal consists of a strawberry yogurt shake, but will not be told the amount provided in the container. The instructions will direct participants to consume as much of the shake as they would like and that the meal will serve as their lunch (or dinner) for the day and to avoid touching or manipulating the container in any way. The meal will be placed on a modified

Protocol Title:	Reward Systems and Food Avoidance in Adolescents with
Trotocor ritie.	Low Weight Eating Disorders
Principal Investigator	[name]
Name/Contact Info:	[contact]; [contact]
Primary Contact	[name]
Name/Contact Info	[contact]; [contact]
Date Revised:	
Study Number:	GCO#15-0939 IF# 2446156 HS# 16-00570

[figure not shown]
version of an eating monitor, which measures intake (in g) every 5 s. During the meal, participants will also be observed through a closed-circuit video monitor to ensure that they are following instructions and to monitor behavior. Ratings will be made before and after the test meal of hunger, fullness, sickness, loss of control, urge to eat, preoccupation with thoughts of food, disgust, and fear of fatness on a 15-cm visual analog scales (VAS). Consumption of the shake in Kcal will be the primary outcome, with secondary outcomes of rate of eating in Kcal/min during the 30 min meal.

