# 1) Objectives:

Protocol Title:	Reward Systems and Food Avoidance in Adolescents with	
	Low Weight Eating Disorders	
Principal Investigator	[name]	
Name/Contact Info:	[contact]; [contact]	
Primary Contact	[name]	
Name/Contact Info	[contact]; [contact]	
Date Revised:		
Study Number:	GCO#15-0939 IF# 2446156 HS# 16-00570	

Our primary objectives are to test our disgust-conditioning model of food avoidance adolescent patients with low-weight eating disorders. We aim to do this by investigating the underlying neurocircuitry involved in food-cue learning and its reversal (i.e., updated learning through reversal of cue-absence vs. cue-target). Our aims are:

- Aim 1: Delineate neurocircuitry through which aversive-disgust responses to palatable food hijack the *acquisition* of food-cue associations in adolescents with LW-EDs versus health controls.
- Aim 2: Characterize the impairments in neurocircuitry that underlies resistance to food-cue *extinction* in adolescents with LW-EDs versus controls.
- Aim 3: Determine the effect of 6-sessions of interoceptive-exposure (IE) and family based therapy for weight regain on neurocircuitry for aversive food-cue *acquisition* and *exposure* in adolescents with LW-EDs.
- Aim 4: Assess the relationship between eating behavior and neurocircuitry for food-cue acquisition and extinction at baseline and following intervention.

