#### **Research Question:**

We have two primary research questions to be investigated in this proposal. First, we are testing for group differences in the underlying neurocircuitry of aversive learning among adolescents with low weight eating disorders and healthy controls and validating this neurocircuitry across multiple domains (psychophysiology of emotion, symptom expression, and objective and real world eating behavior). Our second primary research question is whether interoceptive exposure can modify the connectivity within the neuronetwork that underlies food-cue learning in patients with low-weight eating disorders. We will validate these changes through psychophysiology measures of emotion, symptom change, and measures of objective and real-world eating behavior.

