#### The proposed project will

- (a) use novel fMRI-EMG to test the relationship between effective connectivity within amygdala-insula-ventral striatum network and its relationship to psychophysiological and behavioral measures of acute threat and reward learning in 60 adolescents with LW-EDs and 30 healthy controls.
- (b) test the sensitivity of this network to an experimental interoceptive exposure paradigm relative to patients receiving family based therapy for weight restoration using dynamic causal modeling of fMRI-EMG data pre-post experimental conditions. IE, a behavioral intervention hypothesized to work via altering prefrontal regulation of the insula response to aversive stimuli by decreasing visceral sensitivity, will be compared to a contingency

M
////
Mount
Sinai

Protocol Title:	Reward Systems and Food Avoidance in Adolescents with	
	Low Weight Eating Disorders	
Principal Investigator	[name]	
Name/Contact Info:	[contact]; [contact]	
Primary Contact	[name]	
Name/Contact Info	[contact]; [contact]	
Date Revised:		
Study Number:	GCO#15-0939 IF# 2446156 HS# 16-00570	

management driven family-based weight gain control (FB-WGC) intervention hypothesized to modify the striatal response to food by changing incentive value of food.

(c) validate this model against objective measures of laboratory and real world eating behavior.

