# h) Data Management and Confidentiality

### DATA SHARING PLAN

We will share the primary outcome data from this project with the National Data Archive managed by the National Institutes of Mental Health. The data archive contains anonymized raw data from NIH sponsored programs and research for use in testing reliability of findings from these studies and allowing for future discovery from these data by other investigators or in combination with data collected from other investigators.

Protocol Title:	Reward Systems and Food Avoidance in Adolescents with
	Low Weight Eating Disorders
Principal Investigator	[name]
Name/Contact Info:	[contact]; [contact]
Primary Contact	[name]
Name/Contact Info	[contact]; [contact]
Date Revised:	
Study Number:	GCO#15-0939 IF# 2446156 HS# 16-00570

Our plan will be to upload our primary outcomes which include neuroimaging data (structural scan, BOLD sequence, and task behavioral data) as well as participant weight, eating, and self-report questionnaire data. No identifying information will be shared (e.g., video data, names, address, date of birth). All data will be stored via a unique ID, generated by the data archive that is independent of the unique ID by which data at Mount Sinai is stored. These two IDs will only be stored by the Mount Sinai investigators.

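### Does an endpoint section that names no endpoint let shake intake compete with brain connectivity as the trial's primary outcome?

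*Protocol*

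**What the plan says.** Section 5e (Study Endpoints) is a single sentence about duration: the study should finish "4 years from the date of initial IRB approval including months 43-48 for data analysis". It names no variable, time point or comparison.

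Purpose is stated elsewhere. Under Research Question, the first primary question is whether the neurocircuitry of aversive learning differs between patients and controls, with validation across several domains that include eating. The second is "whether interoceptive exposure can modify the connectivity within the neuronetwork that underlies food-cue learning". For the second question the same section adds: "We will validate these changes through psychophysiology measures of emotion, symptom change, and measures of objective and real-world eating behavior". Item (c) of the list of what the project will do is to "validate this model against objective measures of laboratory and real world eating behavior". Section 1 lists four aims under the primary objectives without ranking them. The fourth is to "Assess the relationship between eating behavior and neurocircuitry for food-cue acquisition and extinction at baseline and following intervention".

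The word *primary* is attached to outcomes in two further places. The single-item meal at Visit 1 (section 5f) states: "Consumption of the shake in Kcal will be the primary outcome, with secondary outcomes of rate of eating in Kcal/min". The Data Sharing Plan (section 5h) says the team will upload "our primary outcomes which include neuroimaging data", and completes the list with "as well as participant weight, eating, and self-report questionnaire data".

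**The concern.** A reader who turns to section 5e to learn what the trial is judged on finds a calendar. The only sentence in the protocol that calls a single variable the primary outcome names shake intake, not connectivity. Read literally, an analyst could report the IE versus FBT-WG difference in shake Kcal as a primary result.

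Shake Kcal is also the measure most open to question in that role. IE sessions use a shake and FBT-WG sessions, as described, do not, so part of any gain in IE could be familiarity with the test. Two rival primary outcomes would also raise the chance of a false positive claim if each were tested without adjustment.

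**Working it through.** **Each use of the word, side by side**

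| Place in protocol | What is called primary | What the text does there |
|---|---|---|
| Section 1, Objectives | testing the food-avoidance model through neurocircuitry; four unranked aims | states purpose |
| Research Question | two questions, both on neurocircuitry or connectivity | states purpose; eating validates |
| Section 5f, single-item meal | shake Kcal | describes one test; the secondary measure is eating rate in that same 30-minute meal |
| Section 5h, Data Sharing Plan | imaging, task behavior, weight, eating and self-report together | lists files to upload |

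The first two rows agree. The third sets one measure of a meal above another measure of the same meal and mentions no comparison between arms. The fourth covers nearly everything collected, so it cannot be a ranking. The item that describes the randomized comparison, (b) in the list of what the project will do, concerns sensitivity of the network, assessed by dynamic causal modeling before and after treatment. No section states a between-arm primary test of shake Kcal.

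**Exposure to the shake**

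Inputs: the visit schedule and the IE and FBT-WG descriptions in section 5f. IE gives a shake in the second hour of session 1 and in each of the 5 remaining sessions, over 30 minutes, in the same form as the first. FBT-WG describes one family meal and no shake. The shake test is at Visits 1 and 9.

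- Study shakes up to and including Visit 9: IE 1 + 6 + 1 = 8; FBT-WG 1 + 0 + 1 = 2.
- In-session shake time between the two tests: IE 6 × 30 = 180 minutes; FBT-WG 0 described.
- Gap from the last IE shake (Visit 8, Day 49) to the test (Visit 9, Day 50 to 57): 50 − 49 = 1 day to 57 − 49 = 8 days.

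The imbalance is real. Whether it is bias is another matter. IE aims to make the sensations of eating tolerable through repeated exposure, so higher intake after six sessions may be the intended effect. The protocol gives no means of separating that from rehearsal.

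Nor is the match between test and treatment complete. The test is eaten freely and described to participants as a strawberry yogurt shake. The IE shake has undisclosed content and comes with instructions and support from therapist and parents.

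**False positives, as an illustration only**

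The protocol gives no significance level. Assuming two independent tests at 0.05 each, the chance of at least one false positive is 1 − 0.95² = 0.0975, or 9.8%. This applies only if both outcomes were declared primary for one claim, which no section does.

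**The case for a change.** The best case for a change is that naming the primary endpoint is the protocol's task, that this protocol has a section for it, and that the section holds something else. An analysis plan can say how an endpoint is analyzed, but the reader should learn from the protocol which one it is. The meal sentence carries no words limiting it to that meal. The multi-item meal at Visit 2 lists its outcomes without rank, so the protocol has no habit of naming a primary measure for each task. Rewording would cost nothing.

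Part of this stands. Section 5e is empty of endpoints, and the two loose uses of the word would read better with their scope stated. It does not carry further, for three reasons.

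- Filling section 5e with the two primary questions would repeat the Research Question section. The choices that could affect a result, such as which connection and which task phase, belong to the analysis plan, which is not at hand.
- Labeling every eating measure secondary would go beyond the text. Aim 4 stands unranked among the aims, and the first primary question itself includes validation against eating.
- Relabeling shake Kcal would leave the 8 versus 2 shakes exactly as they are. Anyone comparing shake intake between arms must weigh that imbalance whatever the label. The multi-item meal, which is not described as part of IE sessions, is the less affected measure of eating.

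**Conclusion.** No change to the plan is called for. The apparent conflict comes from a heading filled with the wrong content, a sentence about one test meal and a data-archiving list. The sections that state what the trial is for consistently point to neurocircuitry and connectivity, with eating as validation, and an analyst would follow them.

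The size of the matter is wording. The exposure counts (8 versus 2 shakes, 180 versus 0 described minutes, 1 to 8 days before the test) are correct but show no error in any planned primary comparison.

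This rests on two assumptions: that the meal sentence is meant within its own test, which is the natural reading but is not spelled out, and that the specific connectivity variable is fixed in an analysis plan before the data are analyzed. If shake Kcal were put forward as the main result between arms, the concern would become substantive.
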